3.2.4. Subject has > Stage II pelvic organ prolapse

- 3.2.5. Subject underwent rectal surgery in the past year
- 3.2.6. Subject has chronic inflammatory bowel disease
- 3.2.7. Subject has diathermy
- 3.2.8. Subject has QTc prolongation
- 3.2.9. Subject has cardiac arrhythmia
- 3.2.10. Subject has other contraindication to SNM.

4.0 SUBJECT REGISTRATION

The Women's Integrated Pelvic Health Program (IPHP) of Northwestern Medicine and Prentice Women's Hospital is a multidisciplinary center with urogynecologists and colon and rectal surgeons specializing in pelvic floor disorders. Women are referred for comprehensive, interdisciplinary evaluation and treatment. Consecutive women undergoing SNM for dual incontinence will be approached for study participation. Consenting participants will complete the short form of the Pelvic Floor Distress Inventory (PFDI-20) as well as 3-day urinary and 7-day bowel diaries to determine eligibility. Women with responses of at least "moderate bother" to PFDI-20 items 10 '*do you lose stool beyond your control if your stool is loose or liquid*' and 16 '*do you experience urine leakage associated with a feeling of urgency that is a strong sensation of needing to go to the bathroom*' will be identified through routine screening in our multidisciplinary clinic.

4.1. Informed Consent (IC) and Institutional Review Board (IRB)

4.1.1. Subject Informed Consent

The Study Coordinator and Principal Investigator will write the Subject Informed Consent Form based off a Northwestern University approved template. The Subject Informed Consent document to be used in this study must be submitted to and approved by the Investigator's IRB prior to screening any potential subjects. Any revisions to the written Informed Consent Form should receive IRB approval in advance of use.

The Site is responsible for obtaining Informed Consent for each subject by having them sign the Subject Informed Consent Form **prior** to performing any test specifically for this study or collecting any data specific to this study. Informed consent will be obtained from the woman participating in the study as well as her partner, who will be filling out questionnaires. Study specific activities include:

- Current Perception Threshold Testing
- GRISS Questionnaire

- FiQOL Questionnaire

In obtaining and documenting informed consent, the Investigator must comply with the applicable regulatory requirement(s), and should adhere to GCP and to the ethical principles that have their origin in the Declaration of Helsinki.

We will waive the documentation of consent process for the male participants in this study. Their only requirement for participation in this study is to complete a questionnaire, which will be administered to them via an online survey through RedCAP, a secure data capture platform. They will receive an email containing the link to the survey, and the body of the email to the male participants will include an online consent document. The male participant will read through this consent and have the option to voluntarily complete the survey, or not to complete the survey by exiting out of the email. We will keep the written consent forms for males that do not have internet or email access.

4.1.2. Institutional Review Board

The IRB is responsible for safeguarding the rights, safety, and well being of all subjects. It is the responsibility of the Investigator to submit all required documentation to the IRB including the Investigational Plan and Subject Informed Consent Form. Written documentation of approval of the Investigational Plan and Subject Informed Consent Form must be provided to the Sponsor **before** starting the registry.

5.0 STUDY DESIGN & METHODS

Summary of Study Design:

	Baseline	Test phase	3 month follow-up
Bladder/bowel diary	X	X	X
Multichannel urodynamics	X		
Endovaginal and endoanal ultrasound	X		
CPT testing	X		X
PFDI	X		X
FISI	X		X
FiQOL	X		X
PISQ-IR	X		X
GRISS	X		X

5.1. Pre-Treatment Evaluation/Baseline

Once the participant and her partner consent, they will undergo a standardized assessment. After the completion of the CPT testing and filling out the required surveys, the participant

will receive a \$50 Prepaid gift card at this initial baseline visit.

5.1.1. Data Collected:

- 5.1.1.1. Age
- 5.1.1.2. Race/Ethnicity
- 5.1.1.3. Medical Co-morbidities
- 5.1.1.4. Prior UUI or FI treatments
- 5.1.1.5. Parity
- 5.1.1.6. Prior Surgery

5.1.2. Standardized Physical Examination Tools:

- 5.1.2.1. Pelvic floor muscle strength using the Oxford scale
- 5.1.2.2. Quantification of pelvic organ prolapsed using POPQ
- 5.1.2.3. Anal Sphincter Tone

5.1.3. Other Examinations Performed

5.1.3.1. 3-D Endovaginal ultrasound

3-D endovaginal ultrasound will be performed using a BK 8838 12mHz, 360degrees rotational transducer (BK Medical, Herlev, Denmark). Women will come in with a comfortably full bladder. In dorsal lithotomy, the ultrasound probe will be inserted into the vagina without excessive pressure. The correct anterior-posterior orientation will be noted using the hyperechogenic aspect of the pubic bone which will be designated the 12 o'clock position, with the anal canal at the 6 o'clock position. The operator will hold the transducer still during the image acquisition that will be performed at a length of 6 cm to scan for 60 seconds. This will yield a 3-D rendered cube to measure the urethra sphincter. This technique has previously been demonstrated^{30,31}

5.1.3.2. 3-D Endoanal ultrasound

3-D Endoanal ultrasound will be performed with a BK 2052 360degrees rotational transducer (BK Medical, Herlev, Denmark). Prior to the endoanal ultrasound exam, women will undergo a digital rectal exam to estimate the orientation of the anal canal. In the dorsal lithotomy position the probe is introduced along the axis of the anal canal until the puborectalis muscle sling is visualized. The anal canal, is divided into three sonographically distinct levels: high, mid, and low. The 3-D rendered cube is obtained at the level of the high anal canal for measurement³².

5.1.3.3. Multichannel urodynamic testing:

All women will undergo standard urodynamic studies according to International Continence Society guidelines.

5.1.3.4. Current Perception Threshold Testing*:

Subjects will undergo CPT testing in a standardized fashion using a Neurometer CPT device in the dorsal lithotomy position. The 2000 Hz frequency will be tested first using the method of limits technique. Next, the amplitude is slowly increased until the stimulus is perceived. This is recorded as the upper limit. Then the stimulus is turned off until the initial sensation subsides. The same stimulus is then slowly decreased until the patient no longer perceives the stimulus. The last stimulus the patient can perceive is termed the lower limit. The upper and lower limits are then averaged to obtain the sensory threshold by the method of limits. The subject is then given a series of forced choice tests by the Neurometer to determine the sensory threshold by the method of levels starting at the lower limit obtained by the method of limits. The Neurometer randomly picks real and false stimuli separated by a 3–5 second rest period. The subject indicated which stimulus was stronger as the intensity was decreased by $0.4\mu\text{A}$ increments. Both the method of limits and the method of levels are then repeated at 250 Hz and 5 Hz.

5.1.4. Questionnaires and Surveys Administered

5.1.4.1. Pelvic Floor Distress Inventory (PFDI-20)³³:

A validated, condition-specific pelvic symptom questionnaire for quantification of pelvic symptoms

5.1.4.2. Fecal Incontinence Severity Index (FISI)³⁴:

A validated questionnaire designed to capture the severity of fecal incontinence symptoms.

5.1.4.3. Pelvic Organ Prolapse Incontinence Sexual Questionnaire, IUGA-revised (PISQ-IR)³⁵:

A validated condition-specific female sexual function questionnaire developed to assess sexual function in women with pelvic floor dysfunction.

5.1.4.4. Golombok Rust Inventory of Sexual Satisfaction (GRISS)³⁶:

A questionnaire developed by sex therapists in the UK in the 1970s for the assessment of the existence and severity of sexual problems³⁹. It can be used to

assess the quality of the sexual relationship of a couple and of an individual's function within a relationship. The GRISS is designated as Grade A (highly recommended) by the Fourth International Consultation on Incontinence. It is easily self administered, allowing for privacy for subjects completing the survey. It takes approximately 15 minutes to complete. The GRISS consists of seven domains, five of which are shared (Non-communication, Infrequency, Dissatisfaction, Avoidance, Non-sensuality) and two of which are gender specific (Vaginismus and Anorgasmia for women, Impotence and Premature Ejaculation for men). Raw scores are transformed to a scaled scores ranging from 1 to 9, with higher scores indicating greater sexual dysfunction. A range of 1 to 4 is considered non-problematic and scores greater than or equal to five are consistent with dysfunction. It is expected that a "normal", functional relationship will yield at least one score of 5 on one of the domains. For this analysis, a score of 5 or more in any category was considered to be consistent with sexual dysfunction.

5.1.4.5. 3-day urinary and 7-day bowel diary

5.1.4.6. Fecal Incontinence Quality of Life Questionnaire:

A validated questionnaire assessing the impact of fecal incontinence on one's quality of life.

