Sacral Neuromodulation in Dual Incontinence: Ultrasound and Afferent Nerve Sensation Assessment

(SaNDI)

PRINCIPAL INVESTIGATOR:

[name], MS
[name]
[name]
[name]
[name]
[contact]

SUB-INVESTIGATORS:

[name]
[name]
[name]
[name]

[name] [name]

Northwestern University

PARTICIPATING SITES:

Northwestern University Feinberg School of Medicine
Department of Obstetrics and Gynecology
Prentice Women's Hospital
[name]
[name]

FUNDING AGENCY:

American Urogynecologic Society

Synopsis

Title	Sacral Neuromodulation in Dual Incontinence: Ultrasound and Afferent Nerve Sensation Assessment
Short Title	SaNDI
Protocol Date	July 7, 2014
Study Duration	1.5 years
Study Center(s)	Northwestern University Feinberg School of Medicine
Objectives	
 1) To quantify the effect of sacral neuromodulation (SNM) on afferent innervation using current perception thresholds (CPT) in women with dual incontinence (urgency urinary incontinence (UUI) and fecal incontinence (FI)). 2) To identify neurophysiologic predictors of successful SNM in women with dual incontinence. 3) To quantify and compare baseline urethral and anal sphincter anatomy as assessed by ultrasound in women with dual incontinence who undergo successful and unsuccessful SNM. 4) To assess the quality of sexual relationships in women with dual incontinence and their male partners and to identify specific areas of dysfunction that are common in these patients.
Number of Subjects	30
Diagnosis and Main Inclusion Criteria	
Women with responses of at least “moderate bother” to PFDI-20 items 10 ‘do you lose stool beyond your control if your stool is loose or liquid’ and 16 ‘do you experience urine leakage associated with a feeling of urgency that is a strong sensation of needing to go to the bathroom’ will be identified through routine screening in our multidisciplinary clinic.
 
Inclusion criteria: Women over the age of 18 with idiopathic dual incontinence planning to undergo placement of a sacral nerve modulator and will be included if they have at least 5 UUI episodes on a 3-day diary and 2 FI episodes on a 7-day diary.

TABLE OF CONTENTS

Synopsis.....	2
1.0. Introduction – Background and Rationale.....	4

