5.4. Three Month Follow up Visit

At the time of this visit, patients who did receive the implanted InterStim will receive an additional \$50 Prepaid gift card for undergoing CPT Testing and filling out surveys at the 3 month follow up visit.

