5.4.1. Questionnaires and Surveys Administered

- 5.4.1.1.** Pelvic Floor Distress Inventory (PFDI-20)³³
- 5.4.1.2.** Fecal Incontinence Severity Index (FISI)³⁴
- 5.4.1.3.** Pelvic Organ Prolapse Incontinence Sexual Questionnaire, IUGA-revised (PISQ-IR)³⁵:
- 5.4.1.4.** Golombok Rust Inventory of Sexual Satisfaction (GRISS)³⁶:
- 5.4.1.5.** 3-day urinary and 7-day bowel diary
- 5.4.1.6.** Fecal Incontinence Quality of Life questionnaire (FiQOL)

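### Applied as an any-domain flag, the GRISS rule in Protocol 5.1.4.4 labels as dysfunctional the relationships that the sentence before it calls normal; the rule should be made domain-specific.

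*Protocol*

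**What the plan says.** Protocol Section 5.1.4.4 describes the GRISS as seven domains per respondent, five common to both sexes and two specific to each sex, scaled from 1 to 9. Three statements then follow one another.

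- Cut-off for a score: 1 to 4 is non-problematic, and "scores greater than or equal to five are consistent with dysfunction".
- Expectation for a normal couple: a "functional relationship will yield at least one score of 5 on one of the domains".
- Rule for this study: "For this analysis, a score of 5 or more in any category was considered to be consistent with sexual dysfunction".

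The same section says that the instrument can "assess the quality of the sexual relationship of a couple and of an individual's function within a relationship", but does not choose between couple and individual for the rule. Objective 4 in the synopsis asks about the quality of sexual relationships and also wants to "identify specific areas of dysfunction that are common in these patients". That objective is not repeated in Section 2.0. Section 6.1 and the SAP carry the same statistical text, and neither mentions the GRISS or sexual function.

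**The concern.** The rule for this study is the only statement in either document on how GRISS scores are to be classified. Its wording fits an overall flag: it refers to any category, and its conclusion is sexual dysfunction without qualification. Used that way, it would be met by couples whom the preceding sentence describes as functional. A proportion with sexual dysfunction built on the flag would then include normal relationships. It would also hide which domain was raised, which is half of what Objective 4 asks for. An analyst who instead took the rule domain by domain would produce a different table from the same data, and the plan gives no ground for choosing between the two.

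**Working it through.** The plan states no GRISS prevalence, sample size or error rate, so there is no figure to reproduce. The check is mainly logical.

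**Step 1. Overall flag, couple as unit.** Flag = 1 if any of the couple's 7 + 7 = 14 scaled scores is 5 or more. A relationship that behaves as the protocol expects has at least one score of 5. Since 5 satisfies 5 or more, the flag is 1. Each such relationship is both normal and flagged.

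**Step 2. Overall flag, person as unit.** Flag = 1 if any of the respondent's 7 scores is 5 or more. The expectation is written for a relationship, so the raised score may belong to either partner. At least one partner in such a couple is flagged, though not necessarily both. The conflict remains but is weaker.

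**Step 3. Domain by domain.** Each domain has its own label, and a score of 5 or more marks that domain only. A functional relationship with one raised domain is then consistent with both sentences. There is no conflict, and the output is the list of areas that Objective 4 wants.

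**Step 4. Which reading does the text favour?** Under Step 3 the study rule repeats the cut-off given two sentences earlier. Under Steps 1 and 2 it adds something. That makes the flag the more natural reading, but not the only one.

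**Step 5. How an any-domain flag accumulates (illustration only).** Let q be an assumed chance that a functional respondent scores 5 or more on one domain, with domains treated as independent. The documents give neither q nor the correlation.

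Person flagged: 1 − (1 − q)^7. Couple flagged: 1 − (1 − q)^14.

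| Assumed q | Person | Couple |
|---|---|---|
| 0.05 | 1 − 0.95^7 = 30% | 1 − 0.95^14 = 51% |
| 0.10 | 1 − 0.90^7 = 52% | 1 − 0.90^14 = 77% |
| 0.20 | 1 − 0.80^7 = 79% | 1 − 0.80^14 = 96% |

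Positive correlation between domains would lower these values. The table shows only that the unit and the number of domains matter; it does not estimate what this trial will see.

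**Step 6. Precision of the domain-specific alternative.** Section 6.2 plans to recruit 15 women and their partners. For x of n, the exact (Clopper-Pearson) 95% limits are the 0.025 quantile of Beta(x, n − x + 1) and the 0.975 quantile of Beta(x + 1, n − x). For 5 of 15, chosen only to show width, these are 0.118 and 0.616, or 12% to 62%.

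**The case against.** The best defence is that the sentence never says overall, person or couple. It may simply adopt the published cut-off for whichever category is being scored, and that suits the wish in Objective 4 to find specific areas of dysfunction. This stands to the extent that the text is ambiguous rather than self-contradictory on every reading. It does not remove the problem, because Objective 4 also asks about the quality of the relationship, and nothing in Section 6.1 or the SAP rules the flag out.

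A second defence is that no stated endpoint, test or sample size uses the flag, and that domain scores are collected in any case. That is correct, and it limits the consequence to a descriptive objective found only in the synopsis.

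Three stronger inferences are tempting and are not supported.

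- A reader might infer that every recruited couple will be flagged. That only restates the protocol's expectation as a certainty. The enrolled women have dual incontinence and are not a sample of functional relationships. Having a partner is not an inclusion criterion, and partners may decline the survey.
- A reader might infer that the trial will report an inflated dysfunction rate. The documents do not say that any overall rate will be reported.
- A reader might infer from Section 4.1.1, where of male partners it says "Their only requirement for participation in this study is to complete a questionnaire", that no partner time point is given. Section 5.1 has the participant and her partner both undergo the baseline assessment once they consent. Only the partner's 3-month assessment is unclear: the Section 5.0 schedule and Section 5.4.1 list the GRISS at 3 months, while Section 4.1.1 speaks of a single questionnaire.

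**Conclusion.** The point holds in a limited form. As an any-domain flag, the rule marks as dysfunctional the relationships that the protocol has just described as normal, and it does not identify the area affected. As a domain-by-domain rule it is sound. The plan does not say which is meant, or whether the unit is the woman, the partner or the couple. The conclusion rests on the adjacent sentences of Section 5.1.4.4 alone and needs no outside figure. The share of couples or people misclassified cannot be determined, because the documents give no per-domain rates and do not say how many enrolled couples would count as functional. The effect is confined to Objective 4 in the synopsis; the primary comparison of current perception thresholds is untouched. It is a secondary correction, worth making before the GRISS data are analysed.

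**What to change.** Replace the any-category sentence in Section 5.1.4.4 with, for example: *Each GRISS domain is analysed separately; a scaled score of 5 or more in a domain is consistent with dysfunction in that domain.* Add a line to Section 6.1 and the SAP that domains are reported separately for women and male partners, with denominators. Do not use the any-domain flag as a dysfunction rate. If it is shown, label it descriptive, state its unit, and note that the protocol expects normal relationships to meet it. State also whether partners repeat the GRISS at 3 months.

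The cost is one replaced sentence, a short addition to the analysis text and a small table, with no new visits or data. What is lost is a single headline rate. Per-domain proportions will be imprecise at the planned recruitment, as the interval for 5 of 15 shows, and less precise still wherever fewer women or partners respond.

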5.2. Stage I Procedure – Test Phase

Study participants will undergo a staged implant procedure as previously described^{37,38}. A quadripolar electrode (Medtronic) will be placed into the sacral foramen (confirmed with fluoroscopy) and connected via a percutaneous extension kit (Medtronic) to an external test stimulator (Medtronic) for approximately 7 days. During the test period, patients will record bladder and bowel diaries. If the number of incontinence episodes is reduced by 50% the patients will undergo placement of a permanent device, InterStim (Medtronic, Minneapolis, MN).

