5.3. Stage II Procedure – Permanent Device Implantation

During Stage II, the patient will undergo implantation of the permanent sacral neuromodulator, InterStim, if symptoms showed 50% improvement during the test phase. This will require a 2-3 day stay in the hospital and will be performed under general anesthesia.

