6.0. STATISTICAL PLAN

6.1. Statistical Analysis:

Each sensory modality threshold as determined at each of the different anatomic sites will be evaluated separately. Sensory thresholds will be compared before and after SNM placement using paired t-test. Multivariate regression models will be used to determine clinical and neurophysiologic predictors of symptom improvement. Urethral sphincter volumes and presence/absence and size of internal and external anal sphincter defects will be compared in responders and non-responders.

6.2. Sample Size Determination:

The sample size estimate was based off data from our prior work and urethral CPT in women with overactive bladder symptoms before and after treatment of tolteradine . Assuming a mean urethral CPT of 1.3 at 250 Hz prior to treatment and a mean of 0.75 after treatment with a standard deviation of 0.66 we estimate that 13 subjects are needed to show a significant difference with a 80% power at 5% significance level. Assuming a 20% dropout rate, we will recruit 15 women and their partners.

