# Cover Page for Data Security Plan

Sponsor Name	Northwestern University
NCT ID	NCT02357784
Sponsor Trial ID	STU00098840
Official Title of the study	Sacral Neuromodulation in Dual Incontinence: Ultrasound and Afferent Nerve Sensation Assessment (SaNDI)
Document Date	2-8-2023

Each sensory modality threshold as determined at each of the different anatomic sites will be evaluated separately. Sensory thresholds will be compared before and after SNM placement using paired t-test. Multivariate regression models will be used to determine clinical and neurophysiologic predictors of symptom improvement. Urethral sphincter volumes and presence/absence and size of internal and external anal sphincter defects will be compared in responders and non-responders.

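### Section 6.2 recruits 15 women for 13 CPT pairs, but its own 20% dropout leaves 12, and it has no term for women who fail the test phase

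*Protocol*

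**What the plan says.** **Sample size.** Protocol 6.2 takes urethral CPT at 250 Hz, with a mean of 1.3 before treatment, 0.75 after and an SD of 0.66, and concludes: "we estimate that 13 subjects are needed to show a significant difference with a 80% power at 5% significance level". It continues: "Assuming a 20% dropout rate, we will recruit 15 women and their partners". It does not say what the 20% covers, what 0.66 is the SD of, or whether the test is one- or two-sided. The synopsis gives 30 subjects.

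**Test-phase gate.** Protocol 5.2 says: "If the number of incontinence episodes is reduced by 50% the patients will undergo placement of a permanent device". Section 5.3 repeats the condition in other terms: "if symptoms showed 50% improvement during the test phase".

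**Who has CPT at 3 months.** The schedule in section 5.0 marks CPT at baseline and at 3 months, with no restriction by implant status. The only text linking 3-month CPT to the implant is the payment sentence in 5.4, where "patients who did receive the implanted InterStim will receive an additional" gift card for CPT and surveys. The 3-month visit also includes a "3-day urinary and 7-day bowel diary".

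**Analysis.** The SAP repeats Protocol 6.1: "Sensory thresholds will be compared before and after SNM placement using paired t-test". Neither says whether placement means the Stage I electrode or the permanent device. For ultrasound, urethral sphincter volumes and "presence/absence and size of internal and external anal sphincter defects will be compared in responders and non-responders"; responder is not defined. The primary objective, 2.1.1, is worded for women with dual incontinence, without mention of test-phase success.

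**The concern.** A paired t-test uses only women measured at both visits, so recruitment has to cover everyone who will lack a second measurement. Section 6.2 does not do this at its own stated loss, and it is silent on a second possible source of loss that the design builds in: women who do not pass the test phase.

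Two things are at stake. The first is the power statement for the primary objective, which is too high under the ordinary reading of the inputs. The second is interpretation. If only implanted women return for CPT, the before–after change is conditional on an early response. That holds at any sample size, and a larger trial would not cure it.

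**Working it through.** **Inputs.** From 6.2: difference 1.3 − 0.75 = 0.55; SD 0.66; 13 pairs; 20% loss; 15 women. Assumptions: two-sided 5%, and 0.66 is the SD of the paired change, so d = 0.55/0.66 = 0.833. From Protocol 1.2.2: SNM success in 60–90% of women with UUI and 90% with FI. These are background success rates, not test-phase pass rates for this population, and serve only as an illustrative range.

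**1. Reproducing the 13.** The normal approximation gives (1.960 + 0.842)²/0.833² = 11.3, so 12. Adding the small-sample correction 1.960²/2 gives 13.2. Exact noncentral-t power is 74.8% at 12 pairs, 78.8% at 13 and 82.2% at 14. The stated 13 is therefore reasonable, at about 79% power.

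**2. Dropout.** Women needed = 13/(1 − 0.20) = 16.25, so 17. Expected pairs from 15 = 15 × 0.80 = 12. With exactly 12 pairs, power is 74.8%. With the number of pairs taken as Binomial(15, 0.80) and power averaged over it, power is 74.1%, and the chance of 13 or more pairs is 40%. Fifteen women yield 13 expected pairs only if total loss is at most 1 − 13/15 = 13.3%. Seventeen women at 20% loss give 13.6 expected pairs and 80% power.

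**3. Dependence on what 6.2 leaves unsaid.**
- One-sided 5%: 12 pairs give 85.5% power.
- If 0.66 is a single-visit SD, the SD of the change is 0.66 × √(2(1 − r)). At r = 0 this is 0.933, and 15 women at 20% loss have 46% power. At r = 0.5 it is 0.66, the main case. At r = 0.75 it is 0.467, and power is 95%.

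**4. Adding the test phase (illustration).** Suppose test failure is additional to the 20% and only implanted women have 3-month CPT. Expected pairs = N × pass rate × 0.80, with power averaged over the binomial as above:

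| Pass rate | Pairs from 15 women | Power | Pairs from 17 women | Power |
|---|---|---|---|---|
| 100% | 12.0 | 74% | 13.6 | 80% |
| 90% | 10.8 | 68% | 12.2 | 75% |
| 60% | 7.2 | 46% | 8.2 | 53% |

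If 90% pass and nobody else is lost, 15 women give 15 × 0.9 = 13.5 expected pairs and 80% power: no shortfall.

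**5. If 30 in the synopsis means women.** At 20% further loss, 30 women give 30 × 0.9 × 0.8 = 21.6 expected pairs (95%) at 90% pass, and 30 × 0.6 × 0.8 = 14.4 (82%) at 60%. Fifteen women and 15 partners also make 30, which fits the wording of 6.2.

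**The case against.** **The dropout gap is small.** This stands as a matter of size: one pair, about five points below the power at 13 pairs. The normal approximation gives 12 pairs with 82% power, and 12/0.8 is exactly 15, which may be where 15 comes from. But 6.2 states 13 and the plan is a t-test, so the printed figures do not agree with each other.

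**The shortfall depends on unstated inputs.** This also stands. A one-sided test or a highly correlated single-visit SD removes it; a single-visit SD with low correlation makes it much worse. That is a reason to state the inputs.

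**The low power figures stack assumptions.** A reader might infer that the trial has under 50% power. The documents do not support that as a finding. It needs the 20% to exclude test failures, which 6.2 does not say; 3-month CPT to be limited to implanted women, which rests on a payment sentence while the schedule shows no restriction; and background success rates to stand in for pass rates.

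**A before–after study of SNM naturally concerns implanted women.** This is fair if placement means the permanent device, and nothing says the result will be extended to women who fail the test. The text still leaves the population open, and 2.1.1 does not narrow it.

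**Test failures may already count as non-responders.** A reader might infer that their baseline data will be lost. No passage says so: objective 2.2.2 compares successful with unsuccessful SNM, and ultrasound is scheduled at baseline. What stands is only that responder is undefined.

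**Conclusion.** The concern holds in a limited form and should be fixed. Section 6.2 misses its own target: 12 expected pairs against 13, and about 74–75% power against the stated 80%, assuming 15 is the number of women, the test is two-sided and 0.66 is the SD of the paired change. If the 20% already includes test failures, that is the whole shortfall.

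The absence of a test-phase term is a real gap of unknown size. The 68% and 46% figures show how much it could matter and are illustrative only. Restriction of the primary result to women who passed the test is likewise conditional on 3-month CPT being limited to implanted women. Confidence is medium, because the main inputs are undefined in the documents.

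**What to change.** 1. **Section 6.2, power.** Restate the power that 15 women deliver at 20% loss (about 74–75% on the assumptions above). State the sidedness and what 0.66 is the SD of. Reconcile 15 women with 30 subjects in the synopsis.
2. **Section 6.2, test phase.** State whether the 20% includes test-phase failure. If it does not, give expected pairs = N × assumed pass rate × (1 − loss after implantation), with power over a range of pass rates labelled as illustrative.
3. **Sections 5.4 and 6.1, and the SAP.** State who has 3-month CPT.
   - If only implanted women do, define the primary comparison as the change from baseline to 3 months among women implanted after a successful test phase, limit the conclusion to them, and tabulate baseline CPT by implant status.
   - If all women return, keep the comparison in implanted women as the effect of ongoing SNM and report non-implanted women separately.
4. **Predictor and ultrasound comparisons.** Define responder. Count test-phase failures as non-responders, shown separately from implanted women without benefit at 3 months. State how implanted women lost before 3 months are classified, for example by test-phase result with a sensitivity analysis. Label these comparisons exploratory.
5. **Sections 5.2 and 5.3.** Reconcile incontinence episodes with symptoms as the basis of the 50% criterion. The implant rule itself is for the investigators.

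The cost is wording plus one descriptive table. These changes disclose the shortfall and do not remove it: no added recruitment is required, but the stated power becomes less favourable and the claim narrower.
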